5.6.1.4 Dose Limiting Toxicity

DLTs were recorded during Cycle 1 (Day 1 to Day 28) for Cohort 1 and during Cycle 1 (Day 1 to Day 21) for Cohort 3A. The DLT (Yes/No) and reason(s) (see [Section 13.1](#)) for each subject will be listed, as well as the date, and dosage of drug when the DLT occurred.

5.6.2 Adverse Events

The AE verbatim descriptions (investigator terms from the eCRF) will be classified into standardized medical terminology using MedDRA version 21.1. Adverse events will be coded to primary System Organ Class (SOC), preferred term (PT) and lower level term (LLT) using MedDRA.

A TEAE is defined as an AE that had an onset date on or after the first dose of study drug up to 30 days following the last dose of study drug, or a worsening in severity from Baseline (pretreatment). In addition, if an AE reemerges during treatment, having been present at pretreatment (Baseline) but stopped before treatment, it is also counted as TEAE. The Common Terminology Criteria for Adverse Events (CTCAE) version 4.03 will be used to assess the severity of AEs.

Only those AEs that are treatment emergent will be included in summary tables. All AEs, treatment emergent or otherwise, will be presented in subject data listings. TEAEs will be summarized by cohort and dose level in Phase 1 and by cohort in Phase 2.

The incidence of TEAEs will be reported as the number (percentage) of subjects with TEAEs within an SOC and PT. Subjects will be counted only once within an SOC and PT, even if the subject experiences more than 1 TEAE within a specific SOC and PT. The number (percentage) of subjects with TEAEs will also be summarized by highest CTCAE grade. The number (percentage) of subjects with treatment-related TEAEs will also be summarized by SOC and PT. Treatment-related TEAEs include those events considered by the investigator to be possibly or probably related to study drug or missing causality.

In summary, the following TEAE tables will be provided:

- Overview of TEAEs
- TEAEs by SOC and PT
- TEAEs in decreasing frequency of PT
- TEAEs by SOC, PT, and CTCAE grade
- TEAEs with CTCAE Grades ≥ 3 by decreasing frequency of PT
- Treatment-related TEAEs by SOC and PT
- Treatment-related TEAEs by SOC, PT, and CTCAE grade
- Treatment-related TEAEs by decreasing frequency of PT
- Treatment-related TEAEs by decreasing frequency of PT with CTCAE Grades ≥ 3
- Treatment-related TEAEs by decreasing frequency of PT with CTCAE Grades 3 or 4
- Treatment-related TEAEs with CTCAE Grades 3 or 4 by SOC and PT
- Grade 5 (fatal) treatment-related TEAEs by decreasing frequency of PT

- Grade 5 (fatal) treatment-related TEAEs by SOC and PT

The following TEAE tables will be provided by age group category (2 to <6 and 6 to <18).

- TEAEs in decreasing frequency of PT by age group
- Serious TEAEs in decreasing frequency of PT by age group

The number (percentage) of subjects with Grade 5 (fatal) TEAEs will be summarized by MedDRA SOC and PT and a subject data listing of all deaths (whether or not treatment emergent) will be provided. All deaths reported will also be summarized in a table.

The number (percentage) of subjects with treatment-emergent SAEs will be summarized by MedDRA SOC and PT. A subject data listing of all SAEs will be provided. The number (percentage) of subjects with TEAEs leading to discontinuation from study drug will be summarized by MedDRA SOC and PT. A subject data listing of all AEs leading to discontinuation, dose modification (reduction or interruption) of study drug will be provided. The number (percentage) of subjects with TEAEs leading to discontinuation, dose reduction, or dose interruption of study drug will also be summarized by MedDRA SOC and PT.

In summary, the following tables will be provided:

- All deaths in the safety analysis set
- Grade 5 (fatal) TEAEs by decreasing frequency of PT
- Grade 5 (fatal) TEAEs by SOC and PT
- Treatment-emergent SAEs by SOC and PT
- Treatment-related treatment-emergent SAEs by SOC and PT
- Treatment-emergent SAEs by decreasing frequency of PT
- Non-fatal treatment-emergent SAEs by SOC and PT
- TEAEs leading to study drug discontinuation by decreasing frequency of PT
- TEAEs leading to study drug discontinuation by SOC and PT
- TEAEs leading to study drug dose reduction and/or dose interruption by decreasing frequency of PT
- TEAEs leading to study drug dose reduction and/or dose interruption by SOC and PT
- TEAEs leading to study drug dose reduction by decreasing frequency of PT
- TEAEs leading to study drug dose reduction by SOC and PT

Clinically significant treatment-emergent AEs (CSAEs) for lenvatinib include arterial TE (thromboembolic) events, cardiac dysfunction, fistula formation, gastrointestinal (GI)

perforation, hemorrhage, hepatotoxicity, hypertension, hypocalcemia, palmar plantar erythrodysaesthesia syndrome (PPE), posterior reversible encephalopathy syndrome (PRES), proteinuria, QT prolongation, renal events, impaired wound healing, weight loss, and pneumothorax. The number and percentage of each category of treatment-emergent CSAEs will be summarized by overall, CTCAE grade and by dose level for Phase 1 and by cohort for Phase 2. Time to first onset of CSAEs for lenvatinib will also be summarized.

The following tables will be provided only for CSAEs.

- Summary of CSAEs by category and PT
- Summary of serious CSAEs by category and PT
- Overview of CSAEs by category
- Incidence and Time to First Onset of CSAEs
- Time to first onset of each CSAE for Lenvatinib
- CSAEs by SOC, PT, and CTCAE grade

The following tables will be provided only for Cohort 1.

- TEAEs in run-in period in decreasing frequency of PT
- TEAEs in run-in period by SOC and PT
- TEAEs in run-in period with CTCAE Grades ≥ 3 by decreasing frequency of PT

The following tables will be provided only for Cohorts 1 and 3A.

- TEAEs in Cycle 1 in decreasing frequency of PT
- TEAEs in Cycle 1 by SOC and PT
- TEAEs in Cycle 1 with CTCAE Grades ≥ 3 by decreasing frequency of PT

The following subject AE listings (treatment-emergent or otherwise) will be provided:

- All AEs
- All deaths for all enrolled subjects
- All SAEs
- All AEs leading to study drug discontinuation
- All AEs leading to dose reduction and / or dose interruption
- All CSAEs

The following subject TEAE listing will be provided only for Cohort 1.

- TEAES in run-in period

The following subject listings will be provided only for Cohorts 1 and 3A.

- DLTs in Cycle 1
- TEAEs in Cycle 1

5.6.3 Laboratory Values

Laboratory values that are nonmissing and reported as "below the detectable limit" of an assay will be replaced by half the detectable limit in the summary tables. Laboratory results will be summarized using *Système international* (SI) units. Laboratory test results will be assigned a low/normal/high (LNH) classification according to whether the value was below (L), within (N), or above (H) the laboratory parameter's reference range. Abnormal laboratory values will be identified as those outside the normal range. The abnormal values will be indicated in data listings. The CTCAE grade will also be included in the listing.

Laboratory tests during treatment are defined as laboratory tests conducted from the start of treatment to no more than 30 days after the last dose of study drug. Only laboratory parameters specified in the protocol will be summarized. Other laboratory parameters collected for some individual subjects will be presented in listings only. Baseline is defined as the last nonmissing result prior to the first administration of study drug.

For quantitative parameters, the actual value and the change from Baseline to each postbaseline visit will be summarized by visit and cohort using descriptive statistics. Qualitative parameters will be summarized using frequencies (number and percentage of subjects), and changes from baseline to the worst postbaseline visit will be reported using shift tables. Percentages will be based on the number of subjects with both nonmissing baseline and relevant postbaseline results.

5.6.3.1 Hematology and Clinical Chemistry

Laboratory parameters will be reported using the following methods for hematology and clinical chemistry:

- Descriptive summary statistics for all major hematology and clinical parameters and their changes from baseline will be calculated (n, mean, SD, median, Q1, Q3, min, max)
- Shifts from Baseline to worst postbaseline visits relative to CTCAE grade (presenting each dose level and overall shift table for all clinical chemistry parameters and the following hematology parameters: hemoglobin, platelets, WBC (leukocytes), neutrophils (ANC), and lymphocytes)

All hematology and clinical chemistry laboratory parameters will be listed by subject and visit.

5.6.3.2 Thyroid-Stimulating Hormone

Thyroid-stimulating hormone values will be summarized in 2 categories (\leq ULN and $>$ ULN) for non-DTC Cohorts 1, 2B, 3A and 3B, and in 3 categories (\leq 0.5, 0.5-5.5 and $>$ 5.5) for DTC Cohort 2A.

5.6.3.3 Urinalysis

The shift of worst postbaseline proteinuria from baseline will be summarized. All urinalysis parameters (RBCs/high-power-field [HPF], blood, and protein [dipstick], 24-hour urine protein) and guaiac fecal occult blood (negative, positive) will be provided by subject listing at each visit.

5.6.4 Vital Signs

Vital signs will be summarized by assessment time and cohort/dose level for Phase 1 or cohort for Phase 2 for the actual value and change from Baseline. Baseline will be defined as the last nonmissing result prior to the first administration of study drug.

Vital sign values will be evaluated on an individual basis by subject. Descriptive statistics for vital sign parameters (systolic [SBP] and diastolic [DBP] blood pressure, pulse rate, respiratory rate, body temperature) and weight and height, as well as changes from Baseline, will be presented by cohort for each cycle and day.

Percentiles for BP values (only for subjects $<$ 18 years old [see Protocol Appendix 7]) will also be summarized using a shift table of worst postbaseline from Baseline measurement by categories ($<$ 90th percentile, 90th to 95th percentile, 95th to \leq 99th percentile, SBP or DBP $>$ 99th percentile). The overall percentile is taken as the worse of SBP/DBP percentiles.

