9.3 Selection of Study Population

Approximately 69 to 108 subjects between 2 and <18 years of age (≤ 25 years for osteosarcoma subjects) will be enrolled at approximately 12 sites in Europe and US. Subjects who do not meet all of the inclusion criteria or who meet any of the exclusion criteria will not be eligible to receive study drug.

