≥ 16 years	1.7	1.4

The threshold creatinine values in this Table were derived from the Schwartz formula for estimating GFR ([Schwartz, et al., 1985](#)) using child length and stature data published by the CDC.

- b. Urine dipstick $< 2+$ for proteinuria. Subjects who have $\geq 2+$ proteinuria on dipstick urinalysis should undergo a spot protein-creatinine (P/C) ratio test that should be Grade < 2 per CTCAE v4.03 and if possible perform a 24-hour urine collection (children and adolescents ≤ 12 years of age must have $\leq 500 \text{ mg}$ of protein/24 hours and subjects > 12 years of age must have $\leq 1 \text{ g}$ of protein/24 hours)
- c. No clinical evidence of nephrotic syndrome

13. Adequate cardiac function as evidenced by left ventricular ejection fraction $\geq 50\%$ at baseline as determined by echocardiography

14. Adequately controlled blood pressure (BP) with or without antihypertensive medications, defined as:

BP <95th percentile for sex, age, and height/length at screening (as per National Heart Lung and Blood Institute guidelines; see [Appendix 7](#) and [Appendix 8](#)) and no change in antihypertensive medications within 1 week prior to Cycle 1/Day 1. Osteosarcoma subjects age 18 to 25 years should have BP \leq 150/90 mm Hg at screening and no change in antihypertensive therapy within 1 week prior to Cycle 1 Day 1.

15. Washout of 3 weeks in case of prior chemotherapy, 6 weeks if treatment included nitrosoureas; 4 weeks for definitive radiotherapy, and 2 weeks for palliative radiotherapy; 3 months from high-dose chemotherapy and stem cell rescue; 3 weeks from major surgery. Subjects must have recovered from the acute toxic effects of all prior anticancer therapy before enrollment into the study
16. Written and signed informed consent from the parent(s) or legal guardian and assent from the minor subject. Written informed consent from subjects \geq 18 years.
17. Willing and able to comply with the protocol, scheduled follow-up, and management of toxicity as judged by the Investigator

Cohort 3B (Combination Expansion): Osteosarcoma subjects who progressed in Cohorts 1 or 2B and opt to receive combination therapy:

18. Osteosarcoma subjects receiving combination therapy of lenvatinib with ifosfamide and etoposide should meet only Inclusion Criteria Numbers 7 6 through 17 (after progression in Cohort 2B)

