9.5.1.5 Safety Assessments

Safety assessments will consist of monitoring and recording all AEs, including all Common Terminology Criteria for Adverse Events (CTCAE) v4.03 grades (for both increasing and decreasing severity), and serious adverse events (SAEs); regular laboratory evaluation of hematology, blood chemistry, and urine values; periodic measurement of vital signs and 12-lead ECGs; and echocardiograms, Lansky play score or Karnofsky performance status score, physical examinations, and height assessments as detailed in the Schedule of Assessments ([Table 7](#), [Table 8](#), and [Table 9](#)). A diary will be provided to each subject to capture any abnormal gastrointestinal symptoms (eg, diarrhea, abdominal discomfort, cramps) experienced during the study. Fecal occult blood will be monitored regularly during the study.

Skeletal bone growth will be assessed by height measurements at the Baseline Visit, thereafter at Day 1 of each cycle during the Treatment Phase for Cohort 1 (and Day 1 of every 3 cycles for cohorts 2A, 2B, 3A and 3B), at the Off-treatment Visit, and every 3 months during the Post-treatment Follow-up for 1 year. Proximal tibial growth plate x-rays will be done at Baseline and at the Off-treatment Visit. Postbaseline, only open growth plates will be further assessed.

Clinical and laboratory toxicities/symptomatology will be graded according to Common Terminology Criteria for Adverse Events (CTCAE) v4.03 (see [Appendix 2](#)).

ADVERSE EVENTS AND OTHER EVENTS OF INTEREST

An adverse event (AE) is any untoward medical occurrence in a subject or clinical investigation in a subject administered an investigational product. An AE does not necessarily have a causal relationship with the medicinal product. For this study, the study drug(s) are lenvatinib, etoposide, and ifosfamide.

The criteria for identifying AEs in this study are:

- Any unfavorable and unintended sign (including an abnormal laboratory finding), symptom, or disease temporally associated with the use of an investigational product, whether or not considered related to the investigational product
- Any new disease or exacerbation of an existing disease. However, worsening of the primary disease should be captured under efficacy assessments as disease progression rather than as an AE.

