5.2.4 Demographic and Other Baseline Characteristics

Demographic and baseline characteristics for the Full Analysis Set will be summarized by cohort using descriptive statistics. Continuous demographic and baseline variables including age (year), height (cm), weight (kg), BMI (kg/m^2) and BSA (m^2), results will be summarized and presented as n, mean, standard deviation, median, Q1, Q3, minimum and maximum values. For categorical variables, the number and percentage of subjects will be used.

Demographics and Baseline categorical variables include age group (2 to <6 years, 6 to <18 years, 6 to <12 years, 12 to <16 years, 16 to <18 years, 18 to ≤ 25 years [Cohorts 2B, 3A and 3B only]), race (White, Black or African American, Asian [Japanese, Chinese, Other Asian], American Indian or Alaska Native, Native Hawaiian or other Pacific Islander, and Other), ethnicity (Hispanic or Latino, not Hispanic or Latino), pregnancy test (present, absent), KPS or Lansky play scores.

Previous anticancer therapy will be summarized by cohort and dose level in Phase 1 and by cohort in Phase 2 as follows:

- Number of previous therapy regimens
- Duration of last medication (months)
- Best response for last anticancer medication (CR, PR, SD, PD, not evaluable, not applicable, unknown)
- Time from end of last anticancer medication to first dose of study drug (months)
- Previous anticancer medication (administered as adjuvant, therapeutic, neoadjuvant, consolidation, maintenance, unknown)
- Previous anticancer procedures (yes, no)
- Time from prior anticancer procedures to first dose (months)
- Prior anticancer medication preferred term

Previous anti-VEGF/VEGFR (vascular endothelial growth factor/vascular endothelial growth factor receptor) therapy will be summarized by cohort and dose level in Phase 1 and by cohort in Phase 2 as follows:

- Number of subjects with any previous VEGF/VEGFR-targeted therapy
- Previous VEGF/VEGFR-targeted therapy (sunitinib, pazopanib, etc.)
- Duration of most recent VEGF/VEGFR-targeted therapy (months)
- Primary reason for discontinuation
- Time from end of most recent VEGF/VEGFR-targeted therapy to first dose of study drug

Prior radiotherapy and radioiodine therapies will be summarized by cohort and dose level in Phase 1 and by cohort in Phase 2 as follows:

- Subjects with any previous radiotherapy
- Tumor lesion at the site progressed since radiotherapy (yes, no, not evaluated)
- Time from last radiotherapy to first dose (months)

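### The one clearly planned aggregate analysis of skeletal growth, raw height change by cohort, cannot tell suppressed growth from completed growth

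*SAP*

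**What the plan says.** Protocol 9.5.1.5 gives height its purpose: "Skeletal bone growth will be assessed by height measurements at the Baseline Visit". Measurements follow on Day 1 of each cycle (Cohort 1) or of every third cycle (the other cohorts), at the Off-treatment Visit, and every 3 months for a year of follow-up. Proximal tibial growth plate x-rays are taken at Baseline and Off-treatment, and after Baseline only open plates are followed. SAP 5.1.2 lists both height and plate closure as safety endpoints.

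For the analysis, SAP 5.6.4 plans descriptive statistics in which "weight and height, as well as changes from Baseline, will be presented by cohort for each cycle and day". The grouping is stated as "Vital signs will be summarized by assessment time and cohort/dose level for Phase 1 or cohort for Phase 2". The section also says "Vital sign values will be evaluated on an individual basis by subject", but gives no growth criterion.

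The plate x-rays are treated in two ways. SAP 5.6 says that they, and their changes from Baseline, will be summarised by cohort as appropriate. SAP 5.6.5.4 and 7.3 say they will only be listed, and 7.3 gives small numbers as the reason.

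On age, Protocol 9.3 admits subjects from 2 to under 18 years, and up to 25 years for osteosarcoma. SAP 5.2.4 marks its 18-to-25 category "years [Cohorts 2B, 3A and 3B only".

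**The concern.** Expected height change over a few months depends on age, sex and whether the plates are still open. A subject whose growth is complete and a growing child whose growth has stopped both contribute zero. A table of raw change by cohort adds these together.

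This matters because Protocol 9.2 describes the trial as the first of lenvatinib in children, and Protocol 7.1.3.1 mentions growth plate toxicity when discussing the drug class. If the only summary table of growth cannot be interpreted, the report can neither raise nor ease that worry from its aggregate data.

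The SAP already accepts the principle elsewhere. In the same section it puts blood pressure on percentiles for subjects under 18. Height gets no such treatment.

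**Working it through.** The documents give no figure for growth, so there is nothing to reproduce. The check has two parts.

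**1. What the documents provide**

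- Standardised height (z-score, percentile or velocity): in neither document.
- Age or sex strata for height: none. The age-group tables in SAP 5.6.2 cover adverse events only, and subgroup analyses are optional and unspecified (SAP 5.3.4).
- Link between height and plate status: none. The open-plate restriction in Protocol 9.5.1.5 applies to x-ray follow-up.
- Subject listing of height: SAP 5.6.4 names none, whereas 5.6.5.1 (ECG) and 5.6.5.2 (LVEF) each do.
- Follow-up heights: the SAP's wording is by cycle and day, so the place of the 3-monthly measurements is unclear.

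**2. Can the mean separate the two explanations?**

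Let c be the share of the cohort with completed growth, s the proportional suppression in those still growing, g the normal growth rate and t the time. Then

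mean height change = (1 − c)(1 − s) × g × t.

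The values of c, s and g are assumptions, since none is in the documents. I take g = 4, 6 and 8 cm/year. For t I use six cycles, the point that sets the data cutoff in SAP 5: 6 × 28 = 168 days (168/365.25 = 0.460 year) for Cohorts 1, 2A and 2B, and 6 × 21 = 126 days (126/365.25 = 0.345 year) for 3A and 3B.

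| Window | g (cm/year) | c = 0, s = 0 | c = 0.5, s = 0 | c = 0, s = 0.5 |
|---|---|---|---|---|
| 24 weeks | 4 | 1.84 cm | 0.92 cm | 0.92 cm |
| 24 weeks | 6 | 2.76 cm | 1.38 cm | 1.38 cm |
| 24 weeks | 8 | 3.68 cm | 1.84 cm | 1.84 cm |
| 18 weeks | 4 | 1.38 cm | 0.69 cm | 0.69 cm |
| 18 weeks | 6 | 2.07 cm | 1.03 cm | 1.03 cm |
| 18 weeks | 8 | 2.76 cm | 1.38 cm | 1.38 cm |

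The last two columns agree in every row because c and s enter the formula symmetrically. The centimetres depend on the assumed growth rate, but the inability to separate c from s does not.

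Restricting to subjects with open plates at Baseline removes c, and an age- and sex-specific reference supplies the expected growth g × t. What remains is departure from expected growth.

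**The case against.** Five points can be made for the plan.

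- **X-rays cover growth.** They are a separate endpoint, and a subject-level listing suits cohorts of about 12, 15 to 30 and 18. This stands in part: a reader could identify closed plates from the listing. But no output joins plate status to height, and the Cohort 3A/3B schedule (Protocol Table 9) makes the x-rays optional in Germany, so some statuses will be unknown.
- **The table is more than a mean.** Quartiles, minimum and maximum are planned, and age groups are tabulated by cohort at Baseline. That gives a rough idea of how many subjects are mature. It does not show which subjects account for the zeros.
- **Individual review is stated.** It is, but without a criterion or a named listing for height.
- **Z-scores have limits here.** There is no control arm, subjects are pretreated, and Cohort 3 adds ifosfamide and etoposide. Protocol 9.4.1 anticipates amputation, which distorts height. This stands.
- **Few subjects will remain.** The design rates for progression-free survival at 4 months imply about 7 to 12 progression-free subjects in 2B (27 × 0.25 = 6.75; 27 × 0.45 = 12.15) and about 4 to 8 in 3B (15 × 0.25 = 3.75; 15 × 0.50 = 7.5). SAP 5.3.6 also drops by-cycle vital-sign summaries once every group has 2 or fewer subjects. This stands, and it makes a subject listing at least as important as the summary.

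A reader might also infer that height is pooled over ages 2 to 25, or that height is the trial's only evidence on growth. The documents support neither. Summaries are by cohort, and by dose level in Phase 1. Subjects of 18 to 25 appear only in 2B, 3A and 3B, and the x-rays are a second measure. Cohorts 1 and 2A are under 18, though they may still mix growing and full-grown adolescents.

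**Conclusion.** The concern holds in a limited form. Raw height and its change from Baseline form the only unambiguously planned aggregate analysis of skeletal growth. In cohorts that mix growing and full-grown subjects, that analysis cannot distinguish suppressed from completed growth. The problem is greatest in 2B, 3A and 3B.

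The conclusion rests on the SAP text and on the symmetry of the formula. The illustrative sizes (for example 1.38 cm under either explanation at 6 cm/year over 24 weeks) rest on an assumed growth rate.

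It would go too far to say that the trial cannot reveal growth impairment at all, since individual x-rays and heights are collected. It would also go too far to expect a z-score to show that lenvatinib caused a deficit, because the design is uncontrolled. This is a descriptive safety endpoint with no decision rule, and the primary analyses are unaffected. The change should be made but is not critical.

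**What to change.** In SAP 5.6.4:

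- Add change from Baseline in sex- and age-specific height z-score. Name the published stature reference and apply it only within its age range; subjects beyond that range keep raw height. The protocol already relies on stature data from one such source for its creatinine limits (Protocol 9.3.1, "using child length and stature data published by the CDC"), though not for growth.
- Include the 3-monthly follow-up heights explicitly.
- Present the result for subjects with open proximal tibial plates at Baseline, and show closed and unknown status separately.
- Add a subject listing of height and z-score beside age, sex, plate status and any lower-limb amputation.

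Reconcile SAP 5.6 (plates summarised by cohort) with 5.6.5.4 and 7.3 (plates listed only).

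The cost is a derivation and one listing. Age, sex, height, surgical history and Baseline x-ray are already in the protocol's assessments, so no new procedure is needed. The drawbacks are small numbers at later visits, missing plate status where the x-ray was optional, and a result that can only be descriptive.
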